Safety criteria:	IRs, anaphylaxis, and immune complex-related adverse events, serious adverse events and adverse event profile, including gout flares
Statistical methods:	
Descriptive statistics will be employed to summarize the proportion of responders, where a responder is defined as a patient whose SUA values were < 6 mg/dL at their final 2 consecutive study visits. Descriptive statistics will be provided for the number of swollen joints and tender joints at baseline, 6 months and 12 months or Early Discontinuation; for changes in numbers of gout flares based on patient reported history at 6-week intervals for Months 1-3 and 3-month intervals thereafter; and for change in the number of tophi at 6 months (Visit 13) and 12 months (Visit 26) or Early Discontinuation.
 
It is anticipated that there may be a considerable number of study patients who will drop out of the study. The sponsor will make every effort to identify the reason(s) for dropout before reaching the primary safety endpoint. For the analysis of each efficacy endpoint, various sensitivity analyses will be performed under different assumptions of potentially informative dropouts. For continuous efficacy variables, sensitivity analyses will be performed using standard mixed-effect model repeated measure (MMRM) methods. All the analyses will be summarized using 95% confidence interval estimates. The resulting summarized statistics for efficacy will be compared to those reported from the pre-approval phase 3 studies.
 
Adverse events will be summarized by presenting the proportion of patients having any adverse event (AE), overall and by body system, and by event as defined by the Medical Dictionary for Regulatory Activities (MedDRA) preferred term. Separate summary tables will be provided for IRs, anaphylaxis AEs, and immune complex-related AEs.
 
For each type of the primary safety endpoints, one event, at most, will be counted per patient. The 95% (exact) confidence interval estimates for each type of safety endpoint will be reported for the rate of incidence both at the administrative interim analysis, for evaluating the feasibility of the study, and at the final analysis. The following hypothesis will be specifically tested: the rate of IRs seen in the phase 3 studies will be reduced in this study by monitoring SUA prior to infusions and

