#### **6.1.5 Efficacy Evaluation**

One efficacy endpoint in this study is normalization of SUA to < 6 mg/dL. Descriptive statistics will be employed to summarize the proportion of responders, where a responder is defined as a patient whose SUA values were < 6 mg/dL at their final 2 consecutive study visits. Summary statistics will be provided for the number of swollen joints and tender joints at baseline, 6 months

(Visit 13) and 12 months (Visit 26) or Early Discontinuation; for changes in numbers of gout flares based on patient reported history at 6-week intervals for Months 1-3 and 3-month intervals thereafter; and for elimination of tophi, i.e., the number of patients with a reported tophus resolution at 6 months (Visit 13) and 12 months (Visit 26) or Early Discontinuation.

It is anticipated that there may be a considerable number of study patients who will drop out of the study. The sponsor will make every effort to identify the reason(s) for dropout before reaching the primary safety endpoint. For the analysis of each efficacy endpoint, various sensitivity analyses will be performed under different assumptions of potentially informative dropouts. For example, in the responder analysis, one analysis will be based on the ITT population with various imputation methods for missing values at the end. Analyses will also be performed assuming all “informative” dropouts are non-responders. For continuous efficacy variables, sensitivity analyses will be performed using standard mixed-effect model repeated measure (MMRM) methods. All the analyses will be summarized using 95% confidence interval estimates. The resulting summarized statistics for efficacy will be compared to those reported from the pre-approval Phase 3 studies.

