### **6.2 Sample Size**

Approximately 1500 patients will be enrolled in order to observe treatment of up to 500 patients for one year. This target sample size is based on clinical judgment and is thought to be adequate to allow for a robust assessment of key safety and efficacy features. No formal statistical sample size calculation has been performed.

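### For joint counts the only named dropout sensitivity analysis is standard MMRM, which assumes missing at random and so cannot show the effect of informative dropout

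*Protocol*

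**What the plan says.** Protocol section 6.1.5 warns: "It is anticipated that there may be a considerable number of study patients who will drop out of the study". It then commits, for each efficacy endpoint, that "various sensitivity analyses will be performed under different assumptions of potentially informative dropouts".

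What follows differs by type of endpoint:

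- **SUA responder (binary).** Two approaches are named: "one analysis will be based on the ITT population with various imputation methods for missing values at the end", and "Analyses will also be performed assuming all “informative” dropouts are non-responders". The second is a genuine departure from missing at random.
- **Continuous efficacy variables.** The only method named is "sensitivity analyses will be performed using standard mixed-effect model repeated measure (MMRM) methods". The synopsis says the same. Neither place gives covariates, a covariance structure, or a rule for placing the Early Discontinuation count in the visit sequence.

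The main analysis of joint counts is descriptive: "Summary statistics will be provided for the number of swollen joints and tender joints at baseline, 6 months" and at 12 months or Early Discontinuation. Protocol section 6.1 leaves further detail to the SAP. The SAP defines analysis populations and lists report contents, but contains no missing-data method, no MMRM specification and no sensitivity analysis.

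**The concern.** Informative dropout means that the unseen values of patients who leave differ from what their observed data predict. A standard MMRM sets that difference to zero. It represents one assumption, and it is the one that the plan says it wants to vary.

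The issue is practical here. Treatment can end because of rising SUA, an infusion reaction or another adverse event (Protocol sections 3.5.2.1 and 3.5.6). Another urate-lowering drug may then be started (section 3.4.5). Joint counts after stopping may therefore follow a different course from those of patients still on pegloticase. There is no control arm against which such a bias could partly cancel, and section 6.1.5 intends to compare the efficacy results with the Phase 3 studies. At stake is whether a favourable 12-month joint-count result would be reported as robust to dropout without having been tested for it.

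**Working it through.** The plan attaches no figure to this point, so there is none to reproduce. The check has three steps.

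**1. Which 12-month joint counts are observed?** Counts are scheduled at screening, Visit 13 (week 25) and Visit 26 (week 51), or at Early Discontinuation (Protocol section 3.6.2.1). A patient who stops early has one count 4 weeks after the last infusion (sections 3.5.3 and 3.5.4). The later follow-up visits cover adverse events, flares, medications and antibodies only (section 3.5.3, additional follow-up; Appendix 3, schedule 2). A patient who stops well before week 51 therefore has no scheduled count at 12 months, even if retained in the study. A late stopper may have one close to it: Visit 24 falls at week 2 × 24 − 1 = 47, and 47 + 4 = 51.

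**2. Size of the effect.** Let p be the fraction without a 12-month count, m_obs the mean in those observed, m_pred the missing-at-random prediction for the rest, and δ the true departure from that prediction.

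- MMRM estimate = (1 − p) × m_obs + p × m_pred
- True mean = (1 − p) × m_obs + p × (m_pred + δ)
- Shift that MMRM cannot show = p × δ

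For p, Protocol section 6.2 states: "Approximately 1500 patients will be enrolled in order to observe treatment of up to 500 patients for one year". Taking 500 completers, 1 − 500/1500 = 0.667. Given that number of completers, 0.667 is an upper bound on p, because some late stoppers have a count near month 12. A lower value of 0.30 is assumed to show the range.

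| p | Shift per 1-joint departure |
|---|---|
| 0.30 (assumed) | 0.30 × 1 = 0.30 joint |
| 0.667 (500 of 1500 complete) | 0.667 × 1 = 0.67 joint |

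**3. Simulation check.** The simulation used 1500 patients, 400 runs per δ, and an outcome with SD 1. Assumed means at baseline, 6 and 12 months were 0, −0.5 and −0.8. Assumed correlations were 0.6 between adjacent visits and 0.5 between baseline and 12 months. Dropout depended on earlier observed values, with 66.7% missing at 12 months. Negative values are improvement. The estimator is the single-arm, unstructured-covariance likelihood estimate.

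| δ (SD) | MMRM | Truth | MMRM − truth |
|---|---|---|---|
| 0 | −0.80 | −0.80 | 0.00 |
| 0.25 | −0.80 | −0.63 | −0.17 |
| 0.50 | −0.80 | −0.47 | −0.33 |
| 0.75 | −0.80 | −0.30 | −0.50 |
| 1.00 | −0.80 | −0.13 | −0.67 |

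The truth moves and the MMRM estimate does not, in line with p × δ. At δ = 0 the completers' mean was −1.30, while MMRM recovered the true −0.80. MMRM therefore does correct dropout that is explained by observed values.

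Steps 2 and 3 suppose that the Early Discontinuation count is not entered in the model as a 12-month value. If it were, few values would be formally missing, and the untested assumption would be that a count 4 weeks after stopping stands for month 12.

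**The case against.** The strongest reply is that section 6.1.5 already promises several sensitivity analyses for every endpoint and does not say that MMRM will be the only one. That is fair: the gap is missing specification of an existing promise, and nothing in the text forbids a further analysis. But section 6.1 sends the detail to the SAP, and the SAP supplies none.

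Several stronger readings are tempting, and the documents do not support them.

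- *The sensitivity analysis shares the main analysis's assumption.* It does not. The main analysis is a descriptive summary that appears to use the Early Discontinuation count. MMRM makes a different assumption, so it is a real contrast, though an incomplete one.
- *SUA is left out of the joint-count model.* No model terms are given, so this cannot be said. What can be said is that a joint-count MMRM would not use SUA unless it is specified.
- *The point applies equally to every efficacy variable.* SUA is scheduled before each infusion and stopping is tied to recorded values, so missing at random may be a reasonable working assumption for SUA itself. Section 6.1.5 treats tophi as the number of patients with resolution, which is binary; only the synopsis describes a change in number.

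The stakes are also limited. Efficacy is secondary, the joint-count analysis is descriptive, and no hypothesis test rests on it.

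**Conclusion.** The point holds for swollen and tender joint counts. The one method named for continuous variables assumes missing at random and cannot show how results change if dropout is informative, which is the stated purpose. MMRM should stay, because it adds something to the descriptive summary.

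The shift of 0.30 to 0.67 joint per 1-joint departure is an illustration. A reader might take 67% as the plan's dropout rate, or 0.67 joint as an expected bias. The documents support neither. The 67% is implied non-completion of one year of treatment if 500 of 1500 complete. The departure, the correlations and the mean changes are all assumed, and the 30% is an assumed lower value. The primary safety objective and the infusion-reaction hypothesis are unaffected.

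**What to change.** In the SAP, before database lock:

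1. Keep MMRM, label it as the missing-at-random analysis, and state its terms, covariance structure and handling of the Early Discontinuation count.
2. Add a delta-adjusted multiple imputation of 12-month swollen and tender joint counts for patients who stopped treatment. Start at the missing-at-random prediction and worsen the imputed values in steps up to a return to baseline. Report the mean change and 95% confidence interval at each step.
3. Put the last on-treatment SUA, the reason for stopping and the Early Discontinuation count in the imputation model.
4. State that the imputed value is the 12-month count regardless of any later urate-lowering therapy.
5. Apply the same to the number of tophi if it is analysed as a count, as in the synopsis.

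A pattern-mixture model by reason for discontinuation would be an acceptable alternative to item 2. The cost is a few extra programmed analyses and a wider reported range for a secondary, descriptive endpoint. No new data are needed: SUA, reason for stopping and the Early Discontinuation count are already collected.

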### **1.2.1 Efficacy Assessments in Clinical Studies of KRYSTEXXA**

The safety and efficacy of KRYSTEXXA® (pegloticase) has been evaluated in 7 clinical studies, including 2 replicate, multicenter, randomized double-blind, placebo-controlled studies of 6-month duration. In the two placebo-controlled studies, adult patients with chronic gout refractory to conventional therapy were randomized to receive intravenous (i.v.) infusions of KRYSTEXXA 8 mg every 2 weeks or every 4 weeks or placebo in a 2:2:1 ratio. All patients also received prophylaxis for infusion reactions (IRs) and for gout flares. To assess the efficacy of KRYSTEXXA in lowering uric acid, the primary endpoint in both trials was the proportion of patients who achieved plasma uric acid (PUA) less than 6 mg/dL for at least 80% of the time during Month 3 and Month 6. A greater proportion of patients treated with KRYSTEXXA every 2 weeks achieved urate lowering to below 6 mg/dL than patients receiving placebo (38% to 47% of patients receiving KRYSTEXXA vs. 0% of patients receiving placebo). In addition, at Month 6, the percentage of patients who achieved a complete resolution of tophi (defined as 100% resolution of at least 1 target tophus, the appearance of no new tophi, and no single tophus showed progression) was 45%, 26% and 8% with KRYSTEXXA 8 mg every 2 weeks, KRYSTEXXA 8 mg every 4 weeks, and placebo, respectively. Although the 4 week regimen also demonstrated efficacy for the primary endpoint, this regimen was associated with an increased frequency of IRs and was less efficacious with respect to tophi. Therefore, pegloticase 8 mg every 2 weeks was approved by the US FDA on September 14, 2010 for the treatment of adult patients with chronic gout refractory to conventional therapy.

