### **3.5.2 Study Procedures**

#### **3.5.2.1 Visits 1 through 26**

At each visit, the following procedures must be completed **before administration of KRYSTEXXA**:

- Provide the KRYSTEXXA Medication Guide and answer any questions the patient has.
- Review concomitant medications, and question patient about any new medical conditions.
- Record all new clinically significant medical conditions in both the medical record and on the adverse event CRF/eCRF and evaluate for the occurrence of an acute gout flare since the previous visit.
- After the first visit, serum uric acid (SUA) levels will be monitored prior to the next infusion and therapy will be discontinued if levels increase above 6 mg/dL on two consecutive measurements. If the SUA is noted to be above 6 mg/dL the sponsor suggests that a repeat SUA should be drawn when the result is noted to confirm, and if the 2 consecutive levels are noted to be above 6 mg/dL then it is advised to discontinue therapy.
- Record blood pressure, heart rate, respiratory rate and temperature shortly before study drug infusion.
- If patient has not had SUA analyzed between his/her last visit and the current one, obtain blood samples for analysis of SUA.
- Record self-administered pre-medications the patient took for prophylaxis against infusion reactions, and administer hydrocortisone (see Section 3.5.8). Record the drug name, dose, route and time of administration of each medication.

**At Visit 1**, but not routinely for other visits, also obtain blood samples for baseline determination of complement components (C3, C4), tryptase level, and identification of antibodies to pegloticase or PEG. These baseline samples will be stored for later analysis to compare with blood samples that are collected at subsequent visits to assess these parameters as part of the evaluation of an IR or potential immune-complex related event (see Section 3.5.8.3).

Following completion of the above procedures:

- Administer KRYSTEXXA (admixed in 250 mL 0.45% or 0.9% Sodium Chloride Injection, USP) by i.v. infusion over 120 minutes. Record the infusion start and finish times, and total volume infused. Details regarding study drug preparation and administration can be found in Section 7.2 and are described in the FDA-approved KRYSTEXXA Full Prescribing Information.
- Follow standard procedures at the center at which the infusion is being performed to monitor for IRs.

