### **3.5.2.3 Visit 27: End of Study**

The final procedures at End of Study (Visit 27) (12 weeks after final KRYSTEXXA infusion) will include:

- Inquire and assess for AEs, gout flares and changes in concomitant medications since previous study visit
- Complete physical exam, reviewing same body systems as at screening visit
- Measure blood pressure, heart rate and temperature
- Collect blood samples for identification of antibodies to pegloticase or PEG
- Record SUA results obtained after the last infusion
- Instruct patients on post-study anti-hyperuricemic therapy as appropriate

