### **3.6 Efficacy Assessments**

#### **3.6.1 Serum Uric Acid Levels**

The efficacy endpoint in this study is normalization of SUA to < 6 mg/dL. Serum uric acid will be measured using a standard clinical assay performed at local laboratories. Blood will be collected several days prior to each KRYSTEXXA infusion for the determination of SUA levels (see Section 3.5.2).

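### The final-two-visits serum urate responder rate is to be compared with a Phase 3 rate that differs in matrix, metric and timing, so the comparison cannot be read as one of urate control

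*Protocol*

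**What the plan says.** **This study.** Protocol Section 6.1.5 (and the synopsis) states that "a responder is defined as a patient whose SUA values were < 6 mg/dL at their final 2 consecutive study visits". Section 3.6.1 adds: "Serum uric acid will be measured using a standard clinical assay performed at local laboratories". On sampling it says: "Blood will be collected several days prior to each KRYSTEXXA infusion for the determination of SUA levels". The last value need not precede an infusion. The End of Study visit instructs sites to "Record SUA results obtained after the last infusion", and the Appendix 3 schedule for early discontinuers has an SUA sample 4 weeks after the last infusion. Section 3.5.4, by contrast, omits SUA for patients who leave the study altogether.

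**Phase 3.** Section 1.2.1 gives the primary endpoint of the two 6-month placebo-controlled studies as "plasma uric acid (PUA) less than 6 mg/dL for at least 80% of the time during Month 3 and Month 6". The result for the two-weekly regimen was "38% to 47% of patients receiving KRYSTEXXA vs. 0% of patients receiving placebo".

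**The comparison.** Section 6.1.5 closes with: "The resulting summarized statistics for efficacy will be compared to those reported from the pre-approval Phase 3 studies". It does not name the Phase 3 statistic, but the rate above is the only Phase 3 urate responder rate in the documents. The SAP asks for counts of patients meeting a primary efficacy criterion at 24 and 52 weeks and does not define that criterion. Neither document gives a matched definition, a re-scoring of the Phase 3 data, or a caveat.

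**The concern.** The two rates answer different questions. One is the share of patients whose last two point values were low, whenever those fell, up to about Week 51. The other is the share whose urate stayed low for most of two fixed months. A patient who is above 6 mg/dL in Month 3 but low at the last two draws passes here and fails in Phase 3. So does a patient who leaves before Month 6 with two low values. A patient controlled in Months 3 and 6 who loses response later does the opposite.

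The plan enrols about 1500 patients to observe up to 500 for a year, and Section 6.1.5 expects considerable dropout, so patients whose last two visits fall well before one year will not be rare. If the two percentages are printed side by side, readers will take the gap between them as information about the drug under SUA monitoring, when part or all of it may come from the definitions.

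**Working it through.** **1. The plan's own figure.** The 38% to 47% cannot be recomputed, because the documents give no numerators or arm sizes. Section 6.1.5 states no test, margin or power for the efficacy comparison, only 95% confidence intervals.

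**2. The definitions side by side.**

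| | This study (3.6.1, 6.1.5) | Phase 3 (1.2.1) |
|---|---|---|
| Matrix | serum, local laboratories | plasma |
| Metric | last two values both below 6 mg/dL | below 6 mg/dL for at least 80% of the time |
| Timing | each patient's own last visits, up to about Week 51 | Months 3 and 6 |
| Early leaver with two low values | responder | no Month 6 control shown; missing-data rule not given |

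**3. Misclassification runs both ways.** Assume a patient is below 6 for a fraction f of the time and the last two values are independent draws. Then P(responder here) = f².
- f = 0.70 fails the 80% rule, yet 0.70² = 49% pass here.
- f = 0.79 fails the 80% rule, yet 0.79² = 62% pass here.
- f = 0.80 meets the 80% rule, yet 1 − 0.80² = 36% fail here.
- f = 0.90 meets the 80% rule, yet 1 − 0.90² = 19% fail here.

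**4. Effect of timing.** Assume all other patients score the same under both rules.
- If 5%, 10% or 20% of patients leave early with two low values and would fail the Phase 3 rule, 38% becomes 43%, 48% or 58%, and 47% becomes 52%, 57% or 67%.
- If instead 5% or 10% pass the Phase 3 rule and lose response by Week 51, 38% becomes 33% or 28%, and 47% becomes 42% or 37%.

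For scale, exact 95% intervals at N = 500 are 33.7% to 42.4% around 38% and 42.6% to 51.5% around 47%, a half-width of about 4.5 points. At N = 1500 they are 35.5% to 40.5% and 44.4% to 49.6%.

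**5. Metric and timing with the stopping rule.** Section 3.5.2.1 says "therapy will be discontinued if levels increase above 6 mg/dL on two consecutive measurements". Assume:
- 25 post-baseline values (Weeks 3 to 51), independent, each below 6 with probability p;
- full adherence to the stopping rule, stopped patients counted as non-responders, no other dropout.

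Let S(n) be the probability of no two consecutive high values among n. Then S(0) = S(1) = 1 and S(n) = p·S(n−1) + p(1−p)·S(n−2).
- Last two of 25 low: p²·S(23).
- All of Weeks 9, 11, 13 and 21, 23, 25 low, with no stop before Week 25: p⁶·S(3)².

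| p | S(23) | Last-two rule | S(3) | Six-value rule |
|---|---|---|---|---|
| 0.95 | 0.9487 | 0.9025 × 0.9487 = 85.6% | 0.9951 | 0.7351 × 0.9903 = 72.8% |
| 0.90 | 0.8160 | 0.8100 × 0.8160 = 66.1% | 0.9810 | 0.5314 × 0.9624 = 51.1% |
| 0.80 | 0.4615 | 0.6400 × 0.4615 = 29.5% | 0.9280 | 0.2621 × 0.8612 = 22.6% |

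The gaps are about 13, 15 and 7 points. The six-value rule is a stand-in. With three values per month, 2 of 3 is 67%, so at least 80% means all three. That can be stricter than 80% of the time.

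**The case against.** The strongest case on the other side has four parts.

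- **The comparison is descriptive.** It serves a secondary objective and has no test, margin or decision rule. This stands: no error rate or sample size is affected, only interpretation.
- **The direction is unknown.** A reader might infer that two values are simply the easier test, so this study will look falsely good. The documents do not support that. Late loss of response, or one chance high value at a final draw, moves patients the other way (steps 3 and 4). A reader might also compare p² with p⁶ directly and find 90% vs 74%, 81% vs 53% and 64% vs 26%. That ignores the stopping rule, which removes many fluctuating patients before their last visits. Independence is itself doubtful: Section 1.2.2 links failure to maintain normal urate to high antibody titres, which suggests persistent rather than random excursions.
- **No rate from this study can truly match Phase 3.** One sample per two-week interval, drawn some days before the infusion, cannot measure time below target, and the Phase 3 missing-data rule is not given. This stands, and it limits any remedy to an approximation.
- **The plan has partial safeguards.** Section 6.1.5 includes an analysis that counts informative dropouts as non-responders, and the SAP tabulates responders at 24 weeks. The first helps with early leavers. The second would help with timing if its criterion were defined. Neither aligns metric or matrix.

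A reader might also infer that this comparison is the planned test of the Section 3.2 premise that stopping on SUA would hardly have changed efficacy. No section says so. Section 3.2 gives the aim of collecting SUA and infusion-reaction data as learning how the two relate.

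**Conclusion.** The point holds as one of comparability. Followed as written, Section 6.1.5 sets a final-two-visits serum rate beside a plasma time-in-target rate, and no conclusion about relative urate control follows from their similarity or difference.

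Neither the direction nor the net size can be fixed from the documents. Both depend on the shares of fluctuating patients, early leavers with low values and late losers of response, none of which is given. Under the assumed shares in step 4, the definitions alone move the rate by 5 to 20 points, at or above the sampling half-width of about 4.5 points at N = 500. The gaps of about 13, 15 and 7 points in step 5 rest on independence, full adherence to the stopping rule, no other dropout, and 80% of three values read as all three. They illustrate possible size and are not a forecast of bias. The consequence is a comparison open to misreading, and it is cheap to improve.

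**What to change.** Keep the final-two-visits endpoint for its own description. For the Phase 3 comparison, add to Section 6.1.5 and to the SAP a second rate from SUA already scheduled at every treatment visit:

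- **Population:** all treated patients. State this explicitly, because the protocol and the SAP define their ITT populations differently.
- **Responder:** estimated share of time below 6 mg/dL of at least 80% in Month 3 and again in Month 6, for example by linear interpolation between successive values. Define the windows by actual draw date, since the sample for a visit falls some days before it.
- **Sensitivity analysis:** all values below 6 mg/dL in both windows. The two versions can differ. With assumed values 3, 6.5 and 3 mg/dL two weeks apart, interpolation puts the patient above 6 for 2 × 2 × (0.5/3.5) = 0.57 of 4 weeks, so 86% of the time is below 6. That patient passes the main version and fails the sensitivity version.
- **Missing data:** a patient without values in a window is a non-responder. Declare this as an assumption.
- **Presentation:** place this rate, with its 95% confidence interval, beside 38% to 47% as an approximate, descriptive comparison. State that serum from local laboratories replaces plasma, that there is one sample per two-week interval, and that Phase 3 missing-data handling may differ.

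The cost is one derived variable and one table, with no new samples or visits. The downside is that the added rate may be less favourable than the final-two-visits rate.
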